4 = Impute January 1 of the stop year

Note: For subjects who were never treated (first dose date is missing), partial start dates will be set to the first day of the partial month.

Note: If the start date imputation leads to a start date that is after the stop date, then do not impute the start date.

Imputation rules for partial or missing stop dates of adverse events and concomitant medications:

- For partial stop date mmyyyy, impute the last day of that month.
- For partial stop date yyyy, impute December 31 of that year.
- For completely missing stop date, do not impute.
- If the stop date imputation leads to a stop date that is after the death date, then impute the stop date as the death date.

- If the stop date imputation leads to a stop date that is before the start date, then there is a data error and do not impute the stop date. (i.e. set the stop date as missing).

Imputation rules for partial or missing new anti-cancer therapy initiation date:

- If the start day of new anti-cancer therapy is missing and month and year are not the same as the last dosing date of study treatment, impute the first day of that month.
- If the start day of new anti-cancer therapy is missing and month and year are same as last dosing date of study treatment, impute the last dosing date of study treatment plus 1 day.
- In other situations, do not impute.

Imputation rules for partial or missing death date:

If death year and month are available but day is missing:

- If mmyyyy for last contact date = mmyyyy for death date, set death date to the day after the last contact date.
- If mmyyyy for last contact date < mmyyyy for death date, set death date to the first day of the death month.
- If mmyyyy for last contact date > mmyyyy for death date, data error and do not impute.
- If both month and day are missing for death date or a death date is totally missing, do not impute.

Note that the last contact date refers to the last contact (i.e. a visit or an assessment) with patient instead of family members. Last contact date would be derived from the latest patient visit/assessment date.

Appendix B. BOR per RECIST 1.1

BOR by investigator will be derived based on the timepoint response collected in the RECIST 1.1 CRF. BOR by central review will be derived from timepoint response shared by the central imaging vendor. At each time point, BOR will be derived based upon the evaluated timepoints up to and including the current MRI/CT assessment. The following rules will apply to BOR:

- CR is better than PR is better than SD is better than PD is better than NE
- For a BOR of SD, a duration of ≥ 35 days since the cycle 1 day 1 is required
- For a BOR of CR or PR confirmation is required. PR can be confirmed by a PR or CR. The confirmation assessment must be in a consecutive assessment ≥ 28 days after the initially observed assessment of CR or PR except the following cases:
 - An unlimited number of intermittent assessments of NE or CR <28 days can occur between the initial response and the confirmation of CR. For example, BL, CR, NE, NE, NE, CR – the CR at post-baseline 1 is confirmed at post-baseline 5. SD is not allowed between CR and subsequent confirmation CR.
 - An unlimited number of intermittent assessments of NE, SD, PR or CR <28 days can occur between the initial response and the confirmation of PR. For example, BL, PR, SD, SD, SD, PR – the PR at post-baseline 1 is confirmed at post-baseline 5.

[Table 14-2](#) provides the BOR determination per RECIST 1.1 where confirmation of response (CR/PR) is required. [Table 14-3](#) outlines the steps to derive Confirmed_BOR (step 1) given timepoint assessments.

At interim analyses (if any), due to lack of sufficient follow-up time for confirmation scan, study team may choose to report both confirmed responders and unconfirmed responders (subjects had an initial PR or CR and still has potential for future confirmative scans). Interim_BOR is defined to include unconfirmed responders in addition to those who achieve Confirmed_BOR. [Table 14-3](#) step 2 provides details to derive the unconfirmed responders.

Table 14-2. BOR per RECIST 1.1 where Confirmation of CR/PR is Required

Criterion	Timepoint T1 Response	T1 ≥ 35 days after C1D1?	Timepoint T2 Response	T2 ≥ 35 days after C1D1?	T2 ≥ 28 days after T1?	BOR_temp
C1	CR	Yes	CR	-	Yes	CR
C2			CR	-	No	SD
C3			PR, SD	-	-	Query data*

C4			PD	-	-	SD
C5			NE, No further evaluations			SD
C6		No	CR	-	Yes	CR
C7			CR	Yes	No	SD
C8			CR	No	No	NE
C9			PR, SD	-	-	Query data*
C10			PD	-	-	PD
C11			NE, No further evaluations			NE
C12	PR	Yes	CR, PR	-	Yes	PR
C13			CR, PR	-	No	SD
C14			SD	-	-	SD
C15			PD	-	-	SD
C16			NE, No further evaluations			SD
C17		No	CR, PR	-	Yes	PR
C18			CR, PR	Yes	No	SD
C19			CR, PR	No	No	NE
C20			SD	Yes	-	SD
C21			SD	No		NE
C22			PD	-	-	PD
C23			NE, No further evaluations			NE
C24	SD	Yes	CR, PR, SD, PD, NE, no more evaluation			SD
C25		No	CR, PR, SD	Yes	-	SD
C26			CR, PR, SD	No	-	NE
C27			PD	-	-	PD
C28			NE, No further evaluations			NE
C29	PD		-			PD
C30	NE	-	NE, No further evaluations			NE
C31		-	CR, PR, SD	Yes	-	SD
C32		-	CR, PR, SD	No	-	NE
C33		-	PD	-	-	PD

*If a CR is truly met at first time point, then any disease seen at a subsequent time point, even disease meeting PR criteria relative to baseline, makes the disease PD at that point (since disease must have reappeared after CR). Best response would depend on whether minimum duration for SD was met. However, sometimes 'CR' may be claimed when subsequent scans suggest small lesions were likely still present and in fact the patient had PR, not CR at the first time point. Under these circumstances, the original CR should be changed to PR. A CR may also be followed by a PR when the target lesion assessment is CR and the non-target lesion assessment is NE. In both of these situations, the best response is PR.

Table 14-3. BOR Derivation Step

Step 1. Derive Confirmed_BOR at each visit

Derive Confirmed_BOR at each visit:

- i) At Visit 1: Use the Visit 1 scan result and refer to [Table 14-2](#) to derive Confirmed_BOR.
- ii) At Visit 2 onward:
 - (a) If current visit is CR: Find last scan that is not NE and at least 28 days before current visit. If current visit is PR: Find last scan that is not NE or SD and at least 28 days before current visit. Derive BOR_temp as below:

Last scan	Current	BOR_temp
CR	CR	CR
PR	CR	PR
PR	PR	PR

- b) If none of above fits, find last scan reference [Table 14-2](#) to derive BOR_temp.

Current visit Confirmed_BOR = best of (BOR_temp, last visit confirmed_BOR). Use rule CR > PR > SD > PD > NE

Step 2. Derive Interim_BOR at last visit prior to DCO	

For subjects who discontinue tumor assessment (i.e. had PD, next therapy, or end of study):
 
Assign Interim_BOR = Confirmed_BOR
	
For subjects with potential for more assessment (i.e. no PD, next therapy, or end of study), unconfirmed PR/CR can be considered responders.
 
 • If any scan is CR and haven't got the opportunity to receive next scan, then Interim_BOR = CR. • If any scan is PR and haven't got the opportunity to receive next scan, then Interim_BOR = PR. • Else, Interim_BOR = Confirmed_BOR at the latest scan.

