11.10.5 Evaluation of Best Overall Response

The subject's best response assignment will depend on the findings of both target and non-target disease and will also take into consideration the appearance of new lesions and confirmation of response. Best overall response (BOR) will be based on all post-baseline disease assessments that occur prior to the initiation of subsequent

anticancer treatment. At least 5 weeks from the first dose of tarlatamab must elapse without radiological disease progression to meet the minimum criteria for SD duration in order to assign a BOR of SD. In general, subjects not classifiable under the RECIST 1.1 response categories due to inadequate data or early death will be classified as non-evaluable (NE) for BOR but will be counted in the denominator of all response rate calculations.

Table 11-5. Time Point Overall Response

Target Lesions	Non-target Lesions	New Lesions	Overall Response
Subjects with Target (± Non-target) Disease			
CR	CR or NA	No	CR
CR	Non-CR/non-PD or NE	No	PR
PR	CR or Non-CR/Non-PD or NE or NA	No	PR
SD	CR or Non-CR/Non-PD or NE or NA	No	SD
PD	Any	Any	PD
Any	PD	Any	PD
Any	Any	Yes	PD
NE	CR or Non-CR/Non-PD or NE or NA	No	NE
Subjects with Non-target Disease Only			
NA	CR	No	CR
NA	Non-CR/Non-PD	No	(Non-CR/Non-PD) ^a
NA	CR or Non-CR/Non-PD	NE	(Non-CR/Non-PD) ^a
NA	PD	Any	PD
NA	Any	Yes	PD
NA	NE	No	NE

CR = complete response; NA = Not applicable; NE = Not evaluable; PD = progressive disease; PR = partial response; RECIST = Response Evaluation Criteria in Solid Tumors; SD = stable disease.

^a Per RECIST 1.1, "SD (Non-CR/Non-PD)" is preferred over "SD" for Non-Target disease since SD is increasingly used as endpoint for assessment of efficacy in some trials so to assign this category when no lesions can be measured is not advised.

Table 11-6. Best Overall Response When Confirmation of Complete Response (CR) and Partial Response (PR) Required

Overall Response First Time Point	Overall Response Second Time Point	Best Overall Response
CR	CR	CR
CR	PR	SD, PD or PR ^a
CR	SD	SD provided minimum criteria for SD duration met, otherwise, PD
CR	PD	SD provided minimum criteria for SD duration met, otherwise, PD
CR	NE	SD provided minimum criteria for SD duration met, otherwise, NE
PR	CR	PR
PR	PR	PR
PR	SD	SD
PR	PD	SD provided minimum criteria for SD duration met, otherwise, PD
PR	NE	SD provided minimum criteria for SD duration met, otherwise, NE
NE	NE	NE

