11.10.7 Confirmation Measurement

Confirmation of CR and PR is required and must occur no fewer than 4 weeks after initial documentation of CR or PR. If CR is pending confirmation and is designated at an assessment followed by 1 or more NE assessments, and/or PR assessments such that the Target Lesion Response is CR and the Non-Target Lesion Response is NE, CR may be confirmed thereafter if Non-Target Lesion Response returns to CR. Similarly, if a PR is pending confirmation and is designated at an assessment followed by 1 or more NE and/or SD assessments, PR may be confirmed thereafter. Subsequent Target Lesion Responses following a CR are limited to CR, PD or NE; PD for target lymph nodes is met only if any lymph node target lesion reaches a short axis measurement of ≥ 15 mm.

11.11 Appendix 11. Specific Guidance for Cytokine Release Syndrome, Immune-effector Cell-associated Neurologic Syndrome, and Tumor Lysis Syndrome

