2.1 Objectives and Endpoints/Estimands

Objectives	Endpoints
Primary	

Evaluate efficacy of tarlatamab as assessed by objective response rate (ORR) based on blinded independent central review (BICR) per Response Evaluation Criteria in Solid Tumors version 1.1 (RECIST 1.1)	
ORR BICR, defined as proportion of subjects with best overall response (BOR) of complete response (CR) or partial response (PR)
Secondary	

Evaluate efficacy of Tarlatamab as assessed by duration of response (DOR), disease control (DC) and progression-free survival (PFS) based on BICR per RECIST 1.1	
DOR, defined as time from the first documentation of objective response (OR) until the first documentation of disease progression or death due to any cause, whichever occurs first. Only subjects who have achieved OR will be evaluated for DORDC, defined as a BOR of CR or PR or stable disease (SD)Duration of DC, defined as time from the first documentation of CR or PR or SD until the first documentation of disease progression or death due to any cause, whichever occurs first. Only subjects who have achieved CR or PR or SD will be evaluated for duration of DCPFS, defined as time from enrolment until disease progression or death from any cause, whichever occurs first. Progression will be based on RECIST 1.1.

Evaluate efficacy of Tarlatamab as assessed by ORR, DOR, DC and PFS based on investigator assessment per RECIST 1.1	
ORR (Investigator)DOR (Investigator)DC (Investigator)Duration of DC (Investigator)PFS (Investigator)

Evaluate efficacy of Tarlatamab as assessed by overall survival (OS)	
OS, defined as time from enrolment until death from any cause

Evaluate safety and tolerability	
Incidence of treatment-emergent adverse events

Characterize the pharmacokinetics of tarlatamab	
Serum concentration of tarlatamab

Evaluate the immunogenicity of tarlatamab	
Incidence of anti-tarlatamab antibody formation

Estimand(s) for Primary Objective(s)

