3.2 Sample Size

Approximately 30 subjects will be enrolled in the study. With 30 subjects enrolled at the target dose, the probability that the observed ORR will be greater than **different thresholds are presented in Table 3.2-1.**

Table 3.2-1. Probabilities of Observed ORR Greater Than Thresholds With Sample Size of 30

True ORR	Probability of Observed ORR > 25 %	Probability of Observed ORR > 30%
0.35	88%	64%
0.4	96%	82%

With 30 subjects, there is a 79% to 96% probability of observing at least 1 adverse event if the true event rate is 5% to 10%.

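### SAP Table 14-2 leaves CR followed by PR or SD as an unrankable data query, and its footnote, read literally, gives PR to an over-called CR followed by SD, or to a CR followed by PR within 28 days

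*SAP*

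**What the plan says.** The primary endpoint is the proportion of subjects with a BOR of CR or PR by BICR (SAP 2.1). Appendix B states: "BOR by central review will be derived from timepoint response shared by the central imaging vendor". Its general rule is: "For a BOR of CR or PR confirmation is required", with the confirming scan at least 28 days after the first.

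In Table 14-2, rows C3 (first scan on or after day 35) and C9 (first scan before day 35) cover a CR followed by PR or SD. Both second responses share one cell, the 28-day column holds a dash, and the output is Query data with an asterisk. The footnote has three branches:

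1. The CR was real. Later disease is PD, and BOR depends on the minimum SD duration.
2. The CR was over-called. The first scan is changed to PR.
3. The later PR is a target CR with non-target NE.

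For branches 2 and 3 it concludes: "In both of these situations, the best response is PR". Table 14-3 then takes the best of the temporary and previous values, ranked CR, PR, SD, PD, NE.

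Protocol Table 11-6 has two separate rows. CR then PR may be SD, PD or PR, with a footnote that carries branches 1 and 2 and points to the confirmation section for timing. CR then SD is "SD provided minimum criteria for SD duration met, otherwise, PD", with no footnote. For a pending CR followed by NE, or by PR with target CR and non-target NE, protocol 11.10.7 says: "CR may be confirmed thereafter if Non-Target Lesion Response returns to CR".

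**The concern.** A derivation table for a primary endpoint should return one defined value for each sequence. C3 and C9 do not. The only text that resolves them is a footnote that names a final answer and does not send the corrected sequence back through the table. Because SD shares the asterisked cell, the footnote reaches a sequence that the protocol handles separately and always as non-response. Because the 28-day cell holds a dash and the timing pointer was dropped, the footnote can also be read as waiving confirmation. Two programmers could therefore derive different BORs from the same scans. SAP section 10, which lists changes from the protocol, does not mention any of this.

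**Working it through.** **Step 1. Does the algorithm return a value?** Table 14-3 step ii(a) lists three pairs: CR-CR, PR-CR and PR-PR. A PR after a CR matches none of them, so it falls to step ii(b) and from there to C3 or C9, even at 28 days or more. A current SD goes straight to ii(b). Query data has no place in the ranking.

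**Step 2. The sequences side by side.**

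| First scan, second scan | SAP footnote read literally | SAP confirmation rows or rule | Protocol |
|---|---|---|---|
| Real CR, then disease | PD at second scan; BOR by SD duration | same | same |
| Over-called CR, PR at 28 days or more | PR | as PR-PR: C12/C17 give PR | PR (Table 11-6 footnote) |
| Over-called CR, PR before 28 days | PR | as PR-PR: C13/C18 give SD, C19 gives NE | 11.10.7 requires at least 4 weeks |
| CR, then PR from target CR with non-target NE, 28 days or more | PR | 28-day rule met | PR is an allowed outcome |
| The same, before 28 days | PR | 28-day rule not met | CR stays pending (11.10.7) |
| Over-called CR, then SD | PR | as PR-SD: C14/C20 give SD, C21 gives NE | SD, otherwise PD |

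The third, fifth and sixth rows disagree. Only the sixth is a direct conflict with a Table 11-6 row.

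**Step 3. When can the under-28-day case occur?** Scans are every 6 weeks ± 1 week to week 48, timed from first dose. The smallest gap between consecutive scheduled scans is (12 − 1) − (6 + 1) = 4 weeks = 28 days, so an unscheduled scan is needed. The earliest scheduled first scan is (6 − 1) × 7 = day 35, so C9 as a whole also needs an unscheduled first scan. Even then ORR changes only if no later scan confirms the response.

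**Step 4. When can an over-called CR be followed by SD?** Let B, S1 and S2 be the target sums at baseline, first and second scan. By protocol Table 11-3, PR at the first scan needs S1 ≤ 0.70B. SD at the second needs S2 > 0.70B and no PD, that is, S2 < 1.2 × S1 or a rise below 5 mm.
- If S2 < 1.2 × S1, then S1 > 0.70B / 1.2 = 0.583B, which is an implausible residue for a scan called CR.
- If the rise is below 5 mm, then B < (S1 + 5)/0.70. For one residual lesion at the 5 mm default (protocol 11.10.6), B < 10/0.70 = 14.3 mm.

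The pattern is possible, but it needs a gross misread or a very small baseline sum.

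**Step 5. Size.** The SAP states: "Approximately 30 subjects will be enrolled in the study". Its Table 3.2-1 reproduces from the exact binomial with n = 30. P(X ≥ 8) is 0.8762 and P(X ≥ 10) is 0.6425 at true ORR 0.35 (stated 88% and 64%). At 0.40 they are 0.9565 and 0.8237 (stated 96% and 82%). One subject is 1/30 = 3.3 points: 12/30 = 40.0% (Clopper-Pearson 95% CI 22.7 to 59.4) against 13/30 = 43.3% (25.5 to 62.6). One subject can also cross a Table 3.2-1 threshold: 7/30 = 23.3% to 8/30 = 26.7%, or 9/30 = 30.0% to 10/30 = 33.3%.

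The documents give no CR rate. Assume that 5 to 10% of subjects have a CR time point and that 10 to 30% of those are followed by PR or SD. The expected number is then 30 × 0.05 × 0.10 = 0.15 to 30 × 0.10 × 0.30 = 0.9. That count includes CR-then-PR at 28 days or more, where there is no disagreement, so the disputed number is smaller and may be 0.

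**The case against.** The strongest reply is that Query data is a cleaning instruction in a temporary column, not a proposed BOR. Protocol 11.10.7 limits target response after a CR to CR, PD or NE, and Table 11-5 gives overall SD only with target SD. CR-then-SD is therefore a data inconsistency, and querying it is sensible. Once the first scan is corrected to PR, rows C12 to C23 apply and the general confirmation rule governs throughout. On that reading nobody gains a response improperly.

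Much of this stands. The sequence should be rare, a query is a reasonable first step, and the confirmation rule is stated plainly. What does not stand is that the SAP says what happens next. It nowhere sends the corrected sequence back to C12 to C23; the footnote states the result itself. If the footnote is taken not to cover SD, then CR-then-SD has no stated outcome until the query is resolved, although the protocol gives it one.

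A reader might also infer that the sponsor will query central reads in one direction, so that ORR is biased upward and BICR loses its independence. The documents do not support this. They do not say who raises or resolves a query on BICR data, the same table serves the investigator's assessments, and the footnote's first branch leads to PD, not to a response.

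**Conclusion.** The point holds as a narrow inconsistency in the derivation of the primary endpoint. Two rows return no rankable value. For an over-called CR followed by SD, the footnote read literally grants a response that the protocol denies. For a CR followed by PR before 28 days, in branches 2 and 3, it grants one without the required confirmation.

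It would be wrong to infer that the footnote turns every CR-then-PR or CR-then-SD into PR, since its real-CR branch does not. It would also be wrong to say that the protocol treats CR-then-PR in general as non-response. Its own footnote gives PR for an over-called CR then PR, and at 28 days or more the documents agree.

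The effect is 3.3 points of ORR per affected subject, with possibly 0 subjects affected. No hypothesis is tested, so only the estimate and its interval are touched. The conclusion rests on a literal reading of the footnote and on scheduled scans keeping to their windows.

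**What to change.** Before database lock:

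- Split C3 and C9 each into a PR row and an SD row.
- Give CR-then-SD the protocol outcome: SD if the minimum duration is met, otherwise PD.
- State that when a CR is re-read as PR, the sequence is re-run through rows C12 to C23 with the 28-day rule. C12 to C16 alone would miss first scans before day 35.
- State that a CR followed by PR because non-target is NE counts as PR only if a PR or CR is seen at least 28 days after the first response. The CR stays open to later confirmation under protocol 11.10.7.
- Restore the pointer to the confirmation rule in the footnote.
- State that for BICR data any re-read belongs to the central reader.

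The cost is a few lines of SAP text and derivation code. Against the literal footnote, the reported ORR can only stay the same or fall slightly.

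### The SAP's step-by-step BOR derivation makes a PR–SD–CR subject a non-responder, although its own confirmation rules make that a confirmed PR

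*SAP*

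**What the plan says.** SAP Appendix B first states confirmation rules in prose, then gives derivation steps in Tables 14-2 and 14-3.

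**The rules.** On what confirms a partial response: "PR can be confirmed by a PR or CR". On what may lie between the initial PR and its confirmation: "An unlimited number of intermittent assessments of NE, SD, PR or CR <28 days can occur". SD is barred only between a CR and the CR that confirms it. Protocol 11.10.7 takes the same line for a PR awaiting confirmation: "followed by 1 or more NE and/or SD assessments, PR may be confirmed thereafter".

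**The steps.** Table 14-3, Step 1(ii)(a), has two look-backs:

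- Current scan CR: "If current visit is CR: Find last scan that is not NE and at least 28 days before current visit".
- Current scan PR: "If current visit is PR: Find last scan that is not NE or SD and at least 28 days before current visit".

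The pair found is read from a three-row table: CR/CR gives CR, PR/CR gives PR, PR/PR gives PR. For any other pair, step (b) applies: "If none of above fits, find last scan reference" Table 14-2. The result is carried forward by "Current visit Confirmed_BOR = best of (BOR_temp, last visit confirmed_BOR").

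**The concern.** The CR branch does two jobs: it confirms an earlier CR, and it confirms an earlier PR (the PR/CR row). Refusing to pass over SD is right for the first job and wrong for the second. A subject with PR, then SD, then CR meets the prose rule for a confirmed PR, but a program written from the steps returns SD.

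This derivation feeds ORR by BICR (the primary endpoint, SAP 9.5.1) and ORR by investigator (SAP 9.5.2). It also decides who is evaluated for DOR, because SAP 5.2 admits only subjects with a confirmed CR or PR. DCR and entry to duration of disease control are not affected, since SD still counts as disease control.

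**Working it through.** The plan gives no figure for this derivation. Its sample-size figures (SAP Table 3.2-1) do reproduce: 87.6% and 64.2% at a true ORR of 0.35, and 95.7% and 82.4% at 0.40. They are not in question.

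**Inputs.** Scans are every 6 weeks ± 1 week to week 48 (Protocol 1.3), so scheduled scans are at least 42 − 14 = 28 days apart and always meet the 28-day condition. The minimum for SD is 35 days from cycle 1 day 1. N = 30.

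**Trace of PR (day 42), SD (day 84), CR (day 126).**

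| Visit | Scan | Route | BOR_temp | Confirmed_BOR |
|---|---|---|---|---|
| 1 | PR | Table 14-2 row C16 | SD | SD |
| 2 | SD | row C14 | SD | SD |
| 3 | CR | look-back finds SD; SD/CR is not in the step (a) table; step (b), row C24 | SD | SD |

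Row C24 covers SD at 35 days or later followed by "CR, PR, SD, PD, NE, no more evaluation", and returns SD in every case. The final BOR is SD. Under the prose rule it is PR: the day-42 PR is followed by one SD, which is permitted, and by a CR 126 − 42 = 84 days later.

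**Neighbouring sequences**, same spacing, using the steps as written and then with the second look-back proposed below:

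| Sequence | As written | With second look-back |
|---|---|---|
| PR–CR | PR | PR |
| PR–NE–CR | PR | PR |
| PR–SD–PR | PR | PR |
| PR–SD–CR | SD | PR |
| PR–SD–SD–CR | SD | PR |
| PR–SD–NE–CR | SD | PR |
| PR–SD–CR–PD | SD | PR |
| PR–SD–CR–CR | CR | CR |
| CR–SD–CR | not a response | not a response |

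**Full comparison.** Tables 14-2 and 14-3 were coded literally and compared with the prose rules over all CR/PR/SD/NE/PD sequences at 42-day spacing, with no PD before the last scan and query-data cases excluded. There is no disagreement at two scans. There is one at three scans (PR–SD–CR). There are seven at four scans: PR–SD–CR–NE, PR–SD–CR–PD, PR–SD–SD–CR, PR–SD–NE–CR, PR–NE–SD–CR, SD–PR–SD–CR and NE–PR–SD–CR. All eight are responders by the rules and non-responders by the steps. The second look-back corrects all eight and creates no new disagreement. These are counts of possible sequences, not of expected subjects.

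**Effect on ORR (Clopper-Pearson 95% CI, n = 30), taking 12 responders by the rules as an illustration.**

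- No subject affected: 12/30 = 40.0% (22.7 to 59.4).
- One affected: 11/30 = 36.7% (19.9 to 56.1).
- Two affected: 10/30 = 33.3% (17.3 to 52.8).

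Each affected subject costs 1/30 = 3.3 points.

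**The case against.** The best defence is that the prose bullets are the governing rules and Table 14-3 only outlines them, so a careful programmer would reach PR and output verification would catch a slip. The SAP, however, sets no order of precedence. SAP 5.2 refers to Appendix B as a whole, and the numbered steps are the part most naturally turned into code.

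A second defence is that not passing over SD is deliberate, because SD may not separate a CR from its confirming CR. That explains the wording, but the same branch also handles a PR confirmed by a CR, where the bar does not apply.

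A third is that Protocol 11.10.7 does not name CR as a scan that can confirm a PR after SD. That is true of that sentence. The SAP says so directly, and Protocol Table 11-6 gives PR followed by CR as PR.

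Several limits do stand:

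- If a confirming CR follows (PR–SD–CR–CR), the steps return CR and the subject counts as a responder.
- If PR or SD follows the CR, row C3 sends the case to a data query.
- If the SD came from an unscheduled scan less than 28 days before the CR (for example days 42, 66, 84), the look-back reaches the PR and returns PR.
- The primary analysis may come at up to 13 weeks of follow-up, and the third scheduled scan falls at week 17 at the earliest. The last subjects enrolled therefore cannot show the pattern on scheduled scans at that analysis. Earlier-enrolled subjects can, and so can anyone by the final analysis.
- No hypothesis is tested and no interim or stopping decision depends on ORR. A shift of 3.3 points is small against an interval about 36 points wide.

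**Conclusion.** The concern holds. Table 14-3 Step 1(ii)(a) contradicts the confirmation rules in the same appendix. The contradiction runs one way: a subject who is a responder by the rules is derived as a non-responder and dropped from DOR. It affects subjects whose PR is followed by SD at least 28 days before a CR, where that CR is then followed by PD, NE, no further scan or the data cut-off.

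The size is 3.3 ORR points per affected subject. How many there will be cannot be taken from the documents, which give neither a CR rate nor a frequency for this path. My assumption is 0 to 1 of 30, because the pattern requires a CR after a lapse to SD; that corresponds to 0 to 3.3 points. The conclusion that the steps are wrong as written does not depend on this assumption. The correction should be made because the steps define the primary endpoint and are easily put right.

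**What to change.** Replace the current-CR instruction in Table 14-3 Step 1(ii)(a) with two look-backs taken in order:

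1. Take the most recent scan at least 28 days earlier that is not NE. If it is CR, BOR_temp = CR.
2. Otherwise, take the most recent scan at least 28 days earlier that is neither NE nor SD. If it is PR, BOR_temp = PR.

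If neither applies, go to Table 14-2 as now. Leave the current-PR instruction unchanged. Apply the same derivation to BICR and investigator BOR, and add PR–SD–CR, PR–SD–CR–PD and CR–SD–CR to the program's test cases (expected: PR, PR, not a response).

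The cost is one sentence in the SAP and one line in the BOR program. No data collection changes. It is best done before the database lock for the primary analysis, so that the rule is not settled with a particular subject's result in view.
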